### **A. General Statistical Methods**

Statistical methodology will consist of summarizing collected data descriptively. Categorical data (e.g., gender or race) will be summarized using counts and percentages, and 95% Confidence Interval (CI), over the time periods of interest. Continuous data, such as age, will be summarized by using means, medians, standard deviation, minimum, maximum, and 95% CI over the time periods of interest. Implant survival and return to function will be summarized using a Kaplan-Meier method and presented with rates (as percentages) and confidence intervals.

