#### **IV. Study Objectives**

The objective of this observational prospective study is to systematically document the clinical outcome of the THP Hip Fracture Plating System when used in fractures of the proximal femur, intracapsular and intertrochanteric fractures, as compared to historical literature data for the same indications when using cannulated or hip screws . These objectives will be assessed using standard scoring systems, radiographic evidence, and adverse event records.

**Safety:** Will be assessed by monitoring the frequency and incidence of adverse events (AE), serious adverse events (SAE), adverse device effects (ADE), serious adverse device effects (SADE), and unanticipated serious adverse device effects (USADE) and device deficiencies.

**Performance:** Will be determined by analyzing the implant survival, overall pain and functional performances on standard scales, subject quality of life, and radiographic parameters of subjects who received the subject device(s). Operative time and readmissions will also be analyzed. Implant survival will be based on removal or intended removal and determined using the Kaplan-Meier method.

- **Overall pain and functional performance** will be based on Visual Analog Scale (VAS) Pain, Rush Score, EuroQol 5D-5L (ED-5D-5L), and Functional Index for Trauma (FIX-IT).
- **Survivorship** will be based on the rate of revision in the study device due to fixation failure or non-union of the femur.
- **Radiographic parameters** to be analyzed may include, but are not limited to, implant fracture, significant implant migration or subsidence, and implant loosening. Other significant findings may also be observed and reported during the course of this study.

It is planned that once sufficient data has been collected allowing meaningful statistical analysis; contributing investigators can use the data for peer reviewed publications, podium presentations and as a basis for surgeon discussions and learning.

**Study Endpoints:** The primary endpoint of this study is defined as the rate of revision after 12 months due to device related complication or non-union of the femur. The secondary endpoints of this study are defined as radiographic and clinical fracture healing of the proximal femur using standard scoring methods.

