## V. Study Design

This is a prospective, multicenter, non-controlled clinical study designed to facilitate the collection and evaluation of pain, function, quality of life, radiographic assessment, and adverse event data. A maximum of 10 sites will contribute to this study to enroll a study maximum of 190 subjects. Enrollment per site will not exceed 57 subjects (30% of the total sample). Each Investigator will be skilled in femur fracture treatment and experienced implanting the devices included in this study, as determined by the Sponsor.

Due to the different historical revision rates for intertrochanteric fractures (~7%) and neck fractures (~20%), study enrollment will be split between the two groups to maintain the integrity of the sample size with an expectant lost to follow-up rate of 15%.

Intertrochanteric fractures will be limited to a maximum of 89 enrolled subjects and intracapsular fractures will be limited to a maximum of 101 enrolled subjects. This will provide enough evaluable data for both indications to show the necessary statistical improvement from the historical revision rates.

Each Principal Investigator will be responsible for obtaining Institutional Review Board (IRB) or Ethics Committee (EC) approval as required prior to conducting the study. In order to avoid potential selection bias, each Investigator will offer study participation to each consecutive eligible patient presenting as a candidate for hip fracture repair using the commercially available (FDA cleared) THP Hip Fracture Plating System. Eligible candidates who express interest in study participation will be offered Informed Consent. All potential study subjects will be required to participate in the Informed Consent process and will not be considered enrolled in the study until the candidate has signed and dated the IRB/EC approved patient Informed Consent. Study data cannot be collected until the candidate has completed the Informed Consent process and signed and dated the IRB or EC approved Informed Consent.

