## **XI. Statistical Considerations**

Performance of the commercially available THP System for treatment of femoral neck fractures or intertrochanteric fractures will be evaluated for fracture healing, pain, function, quality of life, and survivorship. Data collected in this study will be summarized descriptively and descriptive summaries will be the basis of any study reports issued. These summaries may be used for interim study reports and may also be used to support regulatory submissions, presentations, and/or publications. Additional surgical technique and instrumentation data may be collected and evaluated.

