### **B. Sample Size**

Due to the different historical revision rates for intertrochanteric fractures (~7%) and intracapsular fractures (~20%), study enrollment will be split between the two groups to maintain the integrity of the sample size with an expectant lost to follow-up rate of 15%. Intertrochanteric fractures will be limited to a maximum of 89 enrolled subjects and intracapsular fractures will be limited to a maximum of 101 enrolled subjects. This will provide enough evaluable data for both indications to show the necessary statistical improvement from the historical revision rates. The assumed revision rate of the THP Hip Fracture Plating System is 15% for intracapsular fractures and 5% for intertrochanteric fractures with a non-inferiority margin of 8%.

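### The analysis section plans description only, while the sample size rests on a non-inferiority margin and promises improvement; no rule links the planned intervals to the historical rates, and improvement is out of reach at this size

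*Combined protocol and SAP*

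**What the plan says.** The analysis text is explicit. Section XI states "Data collected in this study will be summarized descriptively and descriptive summaries will be the basis of any study reports issued", and Section XI.A opens with "Statistical methodology will consist of summarizing collected data descriptively". XI.A does plan intervals: 95% confidence intervals for categorical and continuous data, and for survivorship "Implant survival and return to function will be summarized using a Kaplan-Meier method and presented with rates (as percentages) and confidence intervals", with no level given for the Kaplan-Meier intervals. None of these is set against a benchmark.

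Other sections go further:

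- Section IV describes the outcome "as compared to historical literature data for the same indications when using cannulated or hip screws" and defines the primary endpoint as "the rate of revision after 12 months due to device related complication or non-union of the femur".
- Section V says the two enrolment caps give "enough evaluable data for both indications to show the necessary statistical improvement from the historical revision rates". Section XI.B repeats this.
- Section XI.B alone gives the design assumptions: historical rates of about 20% (intracapsular) and 7% (intertrochanteric), assumed device rates of 15% and "5% for intertrochanteric fractures with a non-inferiority margin of 8" per cent, and 15% loss to follow-up.

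The synopsis objective is only to document outcomes. No section states a hypothesis, error level, power, success limit, or rule for using the margin.

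**The concern.** Three purposes stand side by side: description (XI, XI.A), improvement on the historical rates (V, XI.B) and non-inferiority within 8 points (XI.B). They need different analyses and very different sample sizes, and the plan does not choose among them. Section XI allows the summaries to support regulatory submissions and publications, so a conclusion about the primary endpoint is likely to be drawn. Under the present text, a statement of non-inferiority would rest on a limit, interval method, confidence level and grouping chosen after the data are seen, so its error rate would not be fixed in advance. A statement of improvement would rest on a sample that was not sized for it.

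**Working it through.** **Inputs.** Sections V and XI.B: enrolment 101 intracapsular and 89 intertrochanteric, loss 15%, historical rates 20% and 7%. Section XI.B only: assumed device rates 15% and 5%, margin 8%. Alpha, sidedness and power are not stated, so the values below are assumptions. The margin is read as absolute, giving limits of 0.20 + 0.08 = 28% and 0.07 + 0.08 = 15%.

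**Evaluable subjects.** 101 × 0.85 = 85.85, about 86. 89 × 0.85 = 75.65, about 76.

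**1. Reproducing the enrolment.** One-sample comparison of a proportion with a fixed limit p0 when the true rate is p1:

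n = [z(1−α)·√(p0(1−p0)) + z(power)·√(p1(1−p1))]² / (p0−p1)², then divide by 0.85.

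With one-sided 5% and 90% power (z = 1.645 and 1.282):

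- Intracapsular: [1.645·√(0.28·0.72) + 1.282·√(0.15·0.85)]² / 0.13² = 84.7 evaluable, 99.6 enrolled.
- Intertrochanteric: [1.645·√(0.15·0.85) + 1.282·√(0.05·0.95)]² / 0.10² = 75.1 evaluable, 88.4 enrolled.

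| Assumed error and power | Intracapsular enrolled | Intertrochanteric enrolled |
|---|---|---|
| Non-inferiority, one-sided 5%, 90% | 99.6 | 88.4 |
| Non-inferiority, one-sided 2.5%, 80% | 97.0 | 91.8 |
| Superiority (p0 = 20%, 7%), one-sided 5%, 90% | 586 | 1,438 |
| Stated in the plan | 101 | 89 |

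The stated sizes therefore fit a non-inferiority comparison that XI.A does not contain. They are far from a superiority comparison.

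**2. Can the design show improvement?** Counts near the assumed rates are 13/86 (15.1%) and 4/76 (5.3%). Their exact two-sided 95% intervals are 8.3-24.5% and 1.5-12.9%. Both include the historical rate (20% and 7%). An exact one-sided 5% test of superiority succeeds only with at most 10/86 or at most 1/76 revisions. At true rates of 15% and 5% the chances are about 24% and 10%. Power of 80% would need about 368 and 910 evaluable subjects.

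**3. Can it show non-inferiority, and under which rule?** The upper limits in step 2, 24.5% and 12.9%, lie below 28% and 15%. Exact binomial rules give:

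| Rule | Intracapsular: maximum revisions, power | Intertrochanteric: maximum revisions, power |
|---|---|---|
| Upper limit of exact two-sided 95% interval | 15/86, 79% | 5/76, 82% |
| Exact one-sided 95% upper limit | 16/86, 86% | 6/76, 91% |

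**4. How much does the unstated interval choice matter?** Upper limits at the boundary counts:

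| Count | Exact two-sided 95% | Exact one-sided 95% | Wald two-sided 95% | Limit |
|---|---|---|---|---|
| 6/76 | 16.4% | 14.99% | 14.0% | 15% |
| 16/86 | 28.4% | 26.9% | 26.8% | 28% |

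At these counts the exact two-sided limit fails and the other two pass. One event fewer and all three pass; one more and all three fail. At the assumed rates the boundary counts occur with probability 9.4% (6/76) and 7.3% (16/86).

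**The case against.** The strongest reply is that XI.A already supplies what is needed. It plans 95% intervals, and an upper limit read against the historical rate plus 8 points is a non-inferiority analysis. Step 3 shows that it would succeed at about the assumed rates. This stands: a reader might infer that no planned analysis could deliver a conclusion, and the documents do not support that. What is absent is the rule for reading the interval, its level, and its use per group.

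Other strong readings also fail:

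- *That IV and V promise non-inferiority.* The margin appears only in XI.B. Section IV speaks of a comparison and Section V of improvement.
- *That the primary rate is pooled.* The endpoint is worded as a single rate, but enrolment is split because the historical rates differ, and the promise covers both indications. A per-group reading is the evident intent; XI.A does not state it.
- *That interval choice broadly reverses the result.* Among the three limits checked, it does so at one count per group.
- *That the sizes contradict two-sided 95% intervals.* One-sided 5% with 90% power fits each group more closely, but one-sided 2.5% with 80% power is also near. With neither stated, no mismatch can be asserted.

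Finally, this is an uncontrolled observational post-market study, for which description is a legitimate aim. That is so, but then the improvement promise and the margin should not stand.

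**Conclusion.** The point holds as a conflict within the current text. The analysis is limited to description, the sample size fits non-inferiority, and the promise is improvement. No passage reconciles these or connects the planned intervals to the historical rates. The larger consequence is the improvement claim: at the plan's own assumed rates the chance of showing it is about 24% (intracapsular) and 10% (intertrochanteric). The missing non-inferiority rule matters less in size, since the choice among the intervals examined changes the verdict only at 16/86 and 6/76, but it leaves the error rate of the primary conclusion unfixed.

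These figures rest on an absolute margin, 86 and 76 evaluable subjects, assumed alpha and power, and simple proportions without censoring.

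**What to change.** Remove the improvement wording from Sections V and XI.B in either case, then choose one route and align Section IV with it.

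**(a) Inferential.** Put non-inferiority wording in V and XI.B in place of improvement. Add to XI.A that the 12-month revision rate is estimated separately for each fracture group with one named interval method and level, and that non-inferiority is concluded only if the upper limit is below the historical rate plus 8 points (28% intracapsular, 15% intertrochanteric). State that the pooled rate is descriptive only. State the power of the chosen rule: about 79% and 82% with the exact two-sided 95% interval, or about 86% and 91% with the exact one-sided 95% limit. If both groups must succeed, and they are independent, the products are 0.788 × 0.820 = 65% and 0.861 × 0.914 = 79%. The maximum counts in the working are illustrative for 86 and 76 subjects without censoring; a Kaplan-Meier estimate with a log-log interval would need its own figures.

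**(b) Descriptive only.** Delete the improvement claim from V and XI.B and the margin from XI.B. State the expected precision per group instead, for example 8.3-24.5% at 13/86 and 1.5-12.9% at 4/76.

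The cost is a paragraph in XI.A and aligned wording elsewhere, with no additional patients. The sponsor gives up choosing the analysis later, and under (a) the stated power may be less favourable than the roughly 90% that the sizes suggest.

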### **B. Sample Size**

Due to the different historical revision rates for intertrochanteric fractures (~7%) and intracapsular fractures (~20%), study enrollment will be split between the two groups to maintain the integrity of the sample size with an expectant lost to follow-up rate of 15%. Intertrochanteric fractures will be limited to a maximum of 89 enrolled subjects and intracapsular fractures will be limited to a maximum of 101 enrolled subjects. This will provide enough evaluable data for both indications to show the necessary statistical improvement from the historical revision rates. The assumed revision rate of the THP Hip Fracture Plating System is 15% for intracapsular fractures and 5% for intertrochanteric fractures with a non-inferiority margin of 8%.

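### The sample size is justified as enough to show improvement over the historical revision rates, but it fits only an 8-point non-inferiority test; power for improvement is about 2–24%

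*Combined protocol and SAP*

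**What the plan says.** Section V describes a single-arm study: "This is a prospective, multicenter, non-controlled clinical study". Section IV defines the primary endpoint as "the rate of revision after 12 months due to device related complication or non-union of the femur" and sets the objective as a comparison with published historical data.

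Sections V and XI.B give historical revision rates of about 20% for intracapsular (neck) fractures and about 7% for intertrochanteric fractures. They cap enrolment at 101 and 89, and expect 15% loss to follow-up. Both sections draw the same conclusion from these figures. In XI.B it reads "This will provide enough evaluable data for both indications to show the necessary statistical improvement from the historical revision rates"; V repeats that the data will be enough "to show the necessary statistical improvement from the historical revision rates".

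The last sentence of XI.B sets the assumed device rates at "15% for intracapsular fractures and 5% for intertrochanteric fractures with a non-inferiority margin of 8" per cent. No alpha, sidedness, power, test or formula is given.

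Section XI.A then states: "Statistical methodology will consist of summarizing collected data descriptively". It provides 95% confidence intervals and Kaplan-Meier summaries, but no hypothesis and no decision rule.

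**The concern.** Improvement and non-inferiority are different hypotheses. Improvement means ruling out a rate of 20% (or 7%) or higher. Non-inferiority with an 8-point margin means ruling out 28% (or 15%) or higher, and a device whose true rate is somewhat worse than the historical one can still pass. XI.B claims the first and supplies parameters for the second. Since the analysis section names neither, nothing in the plan settles which applies.

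This matters in two ways. If the device performs exactly as assumed, the study will probably be unable to make the claim it says it is sized for. And because the plan describes its purpose as showing improvement, a result that is only non-inferior could be reported as improvement. Section XI allows the summaries to support regulatory submissions and publications.

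**Working it through.** **Inputs**

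- From V and XI.B: historical rates 20% and 7%; assumed device rates 15% and 5%; margin 8%; loss 15%; enrolled 101 and 89.
- Assumed, because the plan does not say: the margin is absolute (percentage points); alpha lies between one-sided 2.5% and 5%; each group is tested on its own against a fixed rate.

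Evaluable: 101 × 0.85 = 85.85, about 86; 89 × 0.85 = 75.65, about 76.

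**Step 1. Reproducing the plan's sizes**

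One-sample test of a proportion, null rate p0, true rate p1:

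n = [(z_α √(p0(1−p0)) + z_β √(p1(1−p1))) / (p0−p1)]²

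Non-inferiority nulls: 20% + 8% = 28% and 7% + 8% = 15%. With one-sided 5% (z = 1.645) and 90% power (z = 1.282):

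- Intracapsular, 28% vs 15%: [(0.7385 + 0.4576) / 0.13]² = 84.7, so 85 evaluable; 85 / 0.85 = 100 enrolled (plan: 101).
- Intertrochanteric, 15% vs 5%: [(0.5873 + 0.2793) / 0.10]² = 75.1, so 76 evaluable; 76 / 0.85 = 89.4, so 90 enrolled (plan: 89).

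The total is 190, as planned. At one-sided 2.5% and 80% power the same formula gives 82.5 and 78.0, that is 98 and 93 enrolled. The exact binomial gives 93 and 89 at those settings, which matches one group only.

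**Step 2. Size needed for improvement**

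Same formula with p0 = 20% and 7%, one-sided 5%, 80% power (z = 0.842):

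- Intracapsular: [(0.6579 + 0.3005) / 0.05]² = 367.5, so 368 evaluable; 368 / 0.85 = 433 enrolled.
- Intertrochanteric: [(0.4197 + 0.1834) / 0.02]² = 909.3, so 910 evaluable; 910 / 0.85 = 1071 enrolled.

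At one-sided 2.5% the figures are 471 (555 enrolled) and 1168 (1375 enrolled). That is about 4 times (433/101) to 15 times (1375/89) the planned enrolment.

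**Step 3. Power for improvement at the planned size**

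Exact binomial: find the largest count c with P(X ≤ c | n, p0) ≤ α; power is P(X ≤ c | n, p1).

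| Group | α (one-sided) | c | Exact power | Normal approximation |
|---|---|---|---|---|
| Intracapsular, n = 86 | 5% | 10 | 24.0% | 29.3% |
| Intracapsular, n = 86 | 2.5% | 9 | 15.1% | 18.5% |
| Intertrochanteric, n = 76 | 5% | 1 | 10.1% | 13.0% |
| Intertrochanteric, n = 76 | 2.5% | 0 | 2.0% | 6.8% |

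At one-sided 2.5%, improvement therefore needs at most 9/86 revisions (10.5%), or none in 76. With no loss at all (101 and 89 evaluable), exact power is 23–33% and 6–17%.

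**Step 4. The expected result**

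0.15 × 86 = 12.9 and 0.05 × 76 = 3.8, so about 13 and 4 revisions. The exact 95% intervals are 8.3–24.5% for 13/86 and 1.5–12.9% for 4/76. They contain 20% and 7% respectively.

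**Step 5. What the sizes do support**

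Exact non-inferiority power at 86 and 76 is 86% and 91% at one-sided 5%. It is 79% and 82% at one-sided 2.5%, which corresponds to the two-sided 95% interval.

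**The case against.** The strongest reply is that this is an observational post-market study whose reports rest on descriptive summaries. No planned test fails, no subject's treatment is affected, and the sizes are about right for non-inferiority. On that view, the word improvement is a loose label. It is true that the sizes are adequate for non-inferiority. But the label appears in two sections as the reason for the sample size in both indications, and the absence of a planned test leaves nothing to correct it.

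Several narrower points stand:

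- Alpha, power and test are not documented. The 2–24% range is the exact result under assumed alphas; the normal approximation gives 7–29%.
- The 2% figure is partly an effect of discreteness. At n = 76, one revision has a one-sided p-value of 0.027 and just misses 2.5%. At n = 78 one revision qualifies (0.0239) and power is 9.3%. Likewise, the 91% non-inferiority figure at n = 76 falls to 83% at n = 75, and the expected number is 75.65.
- The intervals in Step 4 are for the expected counts. In about 15% of trials at the assumed rate, the intracapsular interval would lie below 20%.
- Kaplan-Meier estimation uses partial follow-up, so 86 and 76 are approximations. The no-loss figures show how little this could change.
- Confidence intervals and a stated comparison with historical data do exist. What is missing is a rule that links them to the claim.

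**Conclusion.** The concern holds. The statement that 101 and 89 enrolled subjects are enough to show improvement is false for both indications on the plan's own rates. Exact power is 15–24% for intracapsular and 2–10% for intertrochanteric fractures. Across the alphas examined, exact or approximate methods, and zero or 15% loss, it never exceeds about 33%. Of the objectives examined, only non-inferiority with an absolute 8-point margin comes close to both planned sizes. The particular pair of one-sided 5% and 90% power is inferred from the fit, not documented. This should be corrected before any results are interpreted.

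**What to change.** The sponsor should first confirm that non-inferiority is the objective, as the margin and the sizes indicate. Then:

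- **V and XI.B:** replace "to show the necessary statistical improvement from the historical revision rates" with a statement that the data are intended to show a 12-month revision rate less than 8 percentage points above the historical rate, in each indication. State the test, alpha, sidedness and delivered power.
- **XI.A:** add the matching rule. By indication, conclude non-inferiority only if the upper limit of the two-sided 95% confidence interval is below 28% (intracapsular) or 15% (intertrochanteric). Claim improvement only if that limit is below 20% or 7%, and state the low power for that claim.

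The two-sided 95% rule fits the intervals already planned but is stricter than the one-sided 5% that best reproduces the sizes. It gives exact non-inferiority power of about 79% and 82% rather than 86% and 91%, and the protocol should say so. If the sponsor's design alpha was one-sided 5%, it should state that and use the matching interval.

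The cost is wording in two sections and a short decision rule in a third, with no extra subjects. The stated claim becomes less favourable. If improvement is really intended, enrolment would have to rise to about 433 and 1071 (one-sided 5%, 80% power).

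### The single 8-point margin exceeds the ~7% intertrochanteric benchmark, so meeting it excludes only revision rates of 15% or more and cannot support the improvement the plan promises for that group

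*Combined protocol and SAP*

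**What the plan says.** Section IV sets the objective of documenting outcomes "as compared to historical literature data for the same indications when using cannulated or hip screws", with the 12-month revision rate as primary endpoint.

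Section XI.B gives historical revision rates of about 7% for intertrochanteric and about 20% for intracapsular fractures. It assumes rates for the device of "15% for intracapsular fractures and 5% for intertrochanteric fractures with a non-inferiority margin of 8" per cent. One margin serves both groups. Its scale, its rationale, the significance level and the power are not stated.

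On numbers, "Intertrochanteric fractures will be limited to a maximum of 89 enrolled subjects" and "intracapsular fractures will be limited to a maximum of 101 enrolled subjects", "with an expectant lost to follow-up rate of 15" per cent. Sections V and XI.B both explain the split by the difference in historical rates, and both say the evaluable data will be enough, for both indications, "to show the necessary statistical improvement from the historical revision rates".

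The opening of Section XI and Section XI.A plan descriptive summaries, 95% confidence intervals and Kaplan-Meier estimates. No test against the margin and no decision rule is described.

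**The concern.** The plan separates the two groups because their benchmarks differ almost threefold, then gives them the same margin. On the absolute scale, 8 points is 40% of the intracapsular benchmark but 114% of the intertrochanteric one. The intertrochanteric limit of 15% equals the rate the plan assumes for the device in the higher-risk intracapsular group.

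What is at stake is the conclusion drawn for intertrochanteric fractures. Section XI says the summaries may support regulatory submissions and publications. A result that meets the limit shows that revision is below roughly twice the historical rate. The plan's wording would let that be read as improvement on the historical rate, which the margin was not built to show.

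**Working it through.** **Inputs.** From Section XI.B: benchmarks 7% and 20%, assumed device rates 5% and 15%, margin 8%, loss 15%, caps 89 and 101. Assumed, because the plan does not state them: one-sided 5% and 90% power for the reproduction, and both 2.5% and 5% one-sided for the pass rules.

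**Reproducing the caps.** One-sample test of a proportion against a fixed limit p0 = benchmark + 0.08, with true rate p1:

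n = [(z(1−α)·√(p0(1−p0)) + z(power)·√(p1(1−p1))) / (p0 − p1)]², then divided by 0.85.

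- Intertrochanteric, p0 = 0.15, p1 = 0.05: [(0.5873 + 0.2793)/0.10]² = 75.1, and 75.1/0.85 = 88.4. The plan has 89.
- Intracapsular, p0 = 0.28, p1 = 0.15: [(0.7385 + 0.4576)/0.13]² = 84.7, and 84.7/0.85 = 99.6. The plan has 101.

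The other readings tried do not fit both caps under one setting. A relative 8% (limit 7.56%) would need about 917 intertrochanteric subjects. A margin added to the assumed rate (limit 13%) would need about 129. One-sided 2.5% with 80% power gives 93 and 98. The absolute margin added to the historical rate is therefore a well-supported inference.

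**What the limits are.**
- Intertrochanteric: 7 + 8 = 15%, and 15/7 = 2.14 times historical. Twice historical (14%) lies inside the limit.
- Intracapsular: 20 + 8 = 28%, and 28/20 = 1.4 times historical. Twice historical (40%) lies well outside.

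**What a pass requires.** Evaluable: 89 × 0.85 = 75.65, taken as 76. By exact binomial, the largest count that rejects a rate of 15% is 5 at one-sided 2.5% (actual level 0.021) or 6 at one-sided 5% (actual 0.0497). The observed rates are 5/76 = 6.6% and 6/76 = 7.9%. With 75 evaluable the count is 5 at either level.

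| True 12-month rate | Pass, at most 5 events | Pass, at most 6 events |
|---|---|---|
| 5% (assumed) | 82% | 91% |
| 7% (benchmark) | 56% | 72% |
| 10% (1.43 times) | 22% | 35% |
| 12% (1.71 times) | 9% | 18% |
| 14% (2 times) | 4% | 8% |

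**What improvement would require.** The exact two-sided 95% upper limit with 76 evaluable is 4.7% for 0 events, 7.1% for 1, 9.2% for 2, 11.1% for 3, 12.9% for 4 and 14.7% for 5. Only 0 events puts it below 7%. At the assumed 5% the chance of that is 0.95^76 = 0.020. By the formula above with p0 = 0.07 and p1 = 0.05, a study sized for improvement would need about 1,438 enrolled in this group.

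**The case against.** The margin appears once, as a sample-size assumption, and the planned analysis is descriptive. No test is specified and nothing says non-inferiority will be declared. A common absolute margin is a legitimate choice, and nothing in the documents requires the two groups to have the same relative margin. Much of this stands. It means that no particular tighter margin follows from the documents; carrying over the intracapsular ratio (7 × 1.4 = 9.8%) would only be a preference.

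It does not remove the point. The margin fixed the enrolment, and the plan states in two places that this enrolment will show improvement on the historical rates. Descriptive reporting does not make that statement true.

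Three stronger readings are tempting and should be resisted.

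- A reader might infer that a device with twice the historical rate would probably pass. It would not: at 14% the chance is 4% or 8%, and passing needs an observed rate near or below the benchmark.
- A reader might infer that the cohort can never exclude anything below 15%. It can: 4 events in 76, close to the assumed rate, give an upper limit of 12.9%. The 15% is the design limit, and the interval depends on the count.
- A reader might infer that the plan claims the device is as good as historical treatment. It does not use those words; its stated claim is improvement, which a 15% limit supports even less.

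**Conclusion.** The concern holds, for the intertrochanteric group and as a matter of interpretation. The 8-point margin is larger than the benchmark it is added to. Meeting it excludes 12-month revision rates of 15% or more, 2.14 times historical, and does not show improvement on 7%. Improvement would need zero revisions in 76, with a probability of about 2% if the device performs as assumed.

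This rests on the absolute reading of the margin, inferred from the enrolment caps (89 reproduced after rounding up, 100 against 101), on assumed significance levels and power, and on about 76 evaluable subjects. With 75 evaluable the conclusion is the same. The data remain usable; what needs correcting is the claim attached to them.

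**What to change.** Keep enrolment as planned. In Sections V and XI.B, remove the statement about showing improvement on the historical rate as far as it covers intertrochanteric fractures, and write instead:

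> The intertrochanteric 12-month revision rate is estimated with an exact 95% CI and shown against ~7%. The sample size was set to exclude a rate of 15% (7% plus 8 percentage points), about twice the historical rate; meeting this limit will be reported in those words and not as equivalence to, or improvement on, the historical rate. Improvement is claimed only if the upper limit is below 7%.

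Section XI.B should also say that the margin is in absolute percentage points and give the significance level and power used, since the two levels considered here differ by one event (5 or 6 of 76).

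The change is wording in two sections, with no added subjects or visits. The cost is a weaker stated claim for intertrochanteric fractures. Tightening the margin instead would be expensive: at one-sided 5% and 90% power, a 5-point margin (limit 12%) needs about 160 enrolled and a 3.5-point margin (limit 10.5%) about 239, against 89 now.
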